## 1.2 Study Schema

Study design is presented in [Figure 1-1](#).

**Figure 1-1 Study Design**

Note: Adolescent patients will receive treatment in the Lebri Q2W/Q4W arm on an open-label basis and will be separate from the 510 adult participants in this study.

Abbreviations: CFBL = change from baseline; INCS = intranasal corticosteroids; Lebri = lebrikizumab; PBO = placebo; Q2W = every 2 weeks; Q4W = every 4 weeks; Q8W = every 8 weeks.

### **1.3 Schedule of Activities**

The SoA described in [Table 1-1](#) will be followed for all participants enrolled in this study.

**Table 1-1 Schedule of Activities**

CRSwNP 72 Week Visit number	Screening	Run-In	Randomized a Treatment Period								EOT/ET	UV	SFU
	1	2	3	4	5	6	7	8	9	10	11	UV b	801
Weeks from randomization	W-8 to W-4	W-4 to W0	Baseline	W2	W4	W6	W8	W16	W24	W40	W56	NA	W64 or 12 weeks after last dose
Days from randomization	D-58 to D-28	D-28 to D0	D0	D14	D28	D42	D56	D112	D168	D280	D392	NA	D448
Activity Visit interval tolerance (days)	--	--	±3	±3	±3	±3	±3	±3	±3	±5	±5	NA	±5
Informed consent (and assent for adolescents)	X												
Register visit with IWRS	X	X	X	X	X	X	X	X	X	X	X	X	X
Medical history including prior surgeries, prior medications, and prior eye disease history	X												
Substance use (alcohol, nicotine containing products, tobacco)	X												
Vital signs c and weight measurement	X	X	X		X				X	X	X	X	X
Prior treatments for CRSwNP d	X												
Participant demographics	X												
Physical examination (includes height for adults)	X												
Height for adolescents	X		X		X				X	X	X	X	X
Review vaccination status for adolescents c	X												
Review documentation for ruling out cystic fibrosis and primary ciliary dyskinesia for adolescents f	X												
Inclusion and exclusion criteria	X		X										
Chest x-ray e	X												
Treatment													
Randomization (refers to treatment assignment in IWRS)			X										

CRS w NP 72 Week  Visit number  Weeks from randomization  Days from randomization  Activity Visit interval tolerance (days)	Screening	Run-In	Randomized a Treatment Period								EOT/ET	UV	SFU
	1	2	3	4	5	6	7	8	9	10	11	UV b	801
	W-8 to W-4	W-4 to W0	Baseline	W2	W4	W6	W8	W16	W24	W40	W56	NA	W64 or 12 weeks after last dose
	D-58 to D-28	D-28 to D0	D0	D14	D28	D42	D56	D112	D168	D280	D392	NA	D448
	--	--	±3	±3	±3	±3	±3	±3	±3	±5	±5	NA	±5
Dispense and administer IP at clinic h			X	X	X	X	X	X	X	X			
Dispense IP for away dosing h							X	X	X	X			
Train participant and/or caregiver on investigational product administration							X						
Study site dispensing background medication		X	X	X	X	X	X	X	X	X	X		
Procedures													
Nasal endoscopy (NPS) i	X		X		X		X	X	X	X	X	X	
CT scan (sinus) with LMK j			X						X		X		
Spirometry k,r	X		X	X	X		X	X	X	X	X		
UPSIT (Smell Test)			X	X	X			X	X		X		
NPIF f	X	X	X	X	X	X	X	X	X	X	X		
Participant eDiaryl													
Participant eDiary dispensed l		X											
Participant eDiary compliance check m			X	X	X	X	X	X	X	X	X	X	
Participant eDiary return											X		
Patient-Reported Outcomes/Health-Related Quality of Life (electronic device, site-based)													
VAS of CRS			X	X	X		X		X		X	X	
SNOT-22			X		X		X		X	X	X	X	
ACQ-6 n			X		X				X		X	X	
EQ-5D-5L			X						X		X	X	
WPAI+CIQ:CRS w NP			X						X		X	X	

CRSwNP 72 Week  Visit number  Weeks from randomization  Days from randomization  Activity Visit interval tolerance (days)	Screening	Run-In	Randomized a Treatment Period								EOT/ET	UV	SFU
	1	2	3	4	5	6	7	8	9	10	11	UV b	801
	W-8 to W-4	W-4 to W0	Baseline	W2	W4	W6	W8	W16	W24	W40	W56	NA	W64 or 12 weeks after last dose
	D-58 to D-28	D-28 to D0	D0	D14	D28	D42	D56	D112	D168	D280	D392	NA	D448
	--	--	±3	±3	±3	±3	±3	±3	±3	±5	±5	NA	±5
PROMIS Short Form v1.0 – Anxiety 8a			X						X		X	X	
PROMIS Short Form v1.0 – Depression 8a			X						X		X	X	
PGI-S: nasal congestion			X	X	X	X	X	X	X	X	X	X	
PGI-S: loss of smell			X	X	X	X	X	X	X	X	X	X	
PGI-S: postnasal drip			X	X	X	X	X	X	X	X	X	X	
PGI-C: nasal congestion									X		X	X	
PGI-C: loss of smell									X		X	X	
PGI-C: postnasal drip									X		X	X	
Safety													
Adverse events o	X	X	X	X	X	X	X	X	X	X	X	X	X
Concomitant medications	X	X	X	X	X	X	X	X	X	X	X	X	X
Record rescue medication intervention				X	X	X	X	X	X	X	X	X	X
Laboratory Testing													
Pregnancy test (for WOCBP and all female adolescents) p	X		X		X		X	X	X	X	X		X
Hematology/clinical chemistry laboratory	X		X		X		X	X	X	X	X		
Urinalysis	X								X		X		
HCV, HBV, HIV tests	X												
HBV DNA q	X							X	X	X	X		
Immunogenicity (ADA) sample			X		X			X	X		X		X
Total immunoglobulin E			X		X			X	X		X		

Activity	CRSwNP 72 Week	Screening	Run-In	Randomized a Treatment Period							EOT/ET	UV	SFU	
	Visit number	1	2	3	4	5	6	7	8	9	10	11	UV b	801
	Weeks from randomization	W-8 to W-4	W-4 to W0	Baseline	W2	W4	W6	W8	W16	W24	W40	W56	NA	W64 or 12 weeks after last dose
	Days from randomization	D-58 to D-28	D-28 to D0	D0	D14	D28	D42	D56	D112	D168	D280	D392	NA	D448
	Visit interval tolerance (days)	--	--	±3	±3	±3	±3	±3	±3	±3	±5	±5	NA	±5
	Pharmacokinetics s			X		X			X	X	X	X		X
	TB assessment (country-specific) †	X												
Stored Samples														
	Exploratory blood sample biomarkers			X		X			X	X		X		
	Exploratory nasal sample biomarkers			X		X			X	X		X		
	Genetics sample u			X										

Abbreviations: ACQ-6 = Asthma Control Questionnaire-6; ADA = antidrug antibodies; AERD = aspirin-exacerbated respiratory disease; CRS = chronic rhinosinusitis; CRSwNP = chronic rhinosinusitis with nasal polyps; CT = computed tomography; EOT = end of treatment; EQ-5D-5L = EuroQol 5-Dimension 5-Level; ET = early termination; HBV = hepatitis B virus; HBcAb = Hepatitis B antibody; HBsAg = Hepatitis B surface antigen; HCV = hepatitis C virus; ICF = informed consent form; IP = investigational product; IWRS = interactive web response system; LMK = Lund McKay score; NPIF = Nasal Peak Inspiratory Flow; NPS = nasal polyp score; PGI-C = Patient Global Impression of Change; PGI-S = Patient Global Impression of Severity; PRO = patient-reported outcome; PROMIS = Patient-Reported Outcomes Measurement Information System; SFU = safety follow-up; SoA = Schedule of Activities; SNOT-22 = 22-item sino-nasal outcome test; TB = tuberculosis; UPSIT = University of Pennsylvania Smell Identification Test; UV = unscheduled visit; VAS = Visual Analog Scale; WOCBP = women of childbearing potential; WPAI+CIQ:CRSwNP = Work Productivity and Activity Impairment Questionnaire plus Classroom Impairment: chronic rhinosinusitis with nasal polyps.

- Randomization will take place at Visit 3 (baseline) and stratified based on 3 factors: asthma and/or AERD versus no asthma/no AERD, prior nasal polyp surgery versus no prior nasal polyp surgery, geographic region (North America, Europe, rest of the world). Participants will be randomly assigned 1:1:1 using an IWRS to the treatment arms presented in [Section 4.1](#). Eligible adolescent participants will automatically be assigned to the lebrikizumab Q2W/Q4W arm.
- UVs may be conducted to assess efficacy (PROs) and safety before starting any rescue medication ([Section 6.10.3](#)); follow the SoA for procedures required in this scenario. UVs for all other purposes will include activities and procedures at investigator's discretion (see [Section 8](#) for details).
- Includes measurements of blood pressure, pulse, body temperature, and respiratory rate.
- Includes review of medications and procedures.
- The investigator should assess if adolescent participant is up to date with immunizations following the local guidelines for vaccination prior to enrolling into the study. For adolescents who are under vaccinated, the investigator should document the benefit/risk rationale for enrolling the participants in the study.
- The investigator should assess if adolescent participants have cystic fibrosis (CF) and ciliary dyskinesia (PCD) prior to enrolling into the study. The presence of these diagnoses associated with NP will be exclusionary and documentation for ruling them out is required before enrollment.

- g. Chest x-ray is required for participants at screening, unless one has been performed in the previous 12 months and the x-ray and the report is available. For countries that require an x-ray for TB assessment, follow local guidelines ([Section 8.3.7.1](#)).
- h. Participants who are not comfortable self-administering IP away from the study site may come to the study site for administration according to the “away” administration schedule ([Table 6-2](#) and [Table 6-3](#)). Refer to [Section 6.1](#) for details on IP administration.
- i. The endoscopic NPS is assessed by a centralized, blinded, independent review of nasal endoscopy video recordings ([Section 8.2.2](#)).
- j. CT scan will be performed at the ET visit if no postbaseline CT scan had been done.
- k. Spirometry screening for all participants. Any time point after screening is ONLY for participants with asthma ([Section 8.2.4](#)). Spirometry should be performed after withholding the last dose of short-acting bronchodilators for at least 6 hours. If the participant has not followed this instruction, their spirometry measurements for that visit should be rescheduled.
- l. The eDiary will be completed by the participants around the same time each day (preferably in the morning) starting from run-in (Visit 2), and participants will be asked to record the severity of their nasal congestion, loss of smell, postnasal drip, loss of taste, and facial pain/pressure, and rhinorrhea at its worst for the previous 24 hours using their eDiaries ([Section 8.2.1](#), [Section 8.2.5](#), [Section 8.2.6](#), and [Section 8.2.8](#)).
- m. Includes review of dosing eDiaries including background therapy and investigational product injections taken.
- n. ACQ-6 test will be performed in participants who have asthma only.
- o. Includes assessments of all AEs. AEs will be assessed from the time the participant signs the ICF and up until participation in the study has ended ([Section 8.3.1](#)).
- p. Pregnancy tests will be conducted only for individuals of childbearing potential and all female adolescents: serum testing at screening and urine testing at subsequent visits prior to administering any IP. Refer to [Section 8.4](#) for details on reporting positive pregnancy test results obtained away from the study site. Additional pregnancy tests (beyond those required by the SoA) should be performed at any time during the study if a menstrual period is missed or there is clinical suspicion of pregnancy. If required per local regulations and/or institutional guidelines, pregnancy testing can occur at other times during the study treatment period.
- q. If HBsAg is negative and HBcAb is positive at screening, further testing for HBV DNA is required ([Section 7.1](#), [Section 7.1.2](#), [Section 7.2.1](#), and [Section 8.3.7.6](#), and [Appendix 15.2](#) and [Appendix 15.4](#)).
- r. NPIF and spirometry should be performed prior to endoscopy.
- s. Blood samples will be collected before dosing of IP on a dosing day.
- t. For countries that require an additional TB assessment (ie, QuantiFERON), local guidelines will be followed.
- u. Genetic samples will be collected for exploratory research where local regulations allow ([Section 8.9](#)).

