**Table 6-2 Loading Dose and Induction Period Dosing Schedule**

Week	W0 Clinic	W2 Clinic	W4 Clinic	W6 Clinic	W8 Clinic	W10 Away	W12 Away	W14 Away	W16 Clinic	W18 Away	W20 Away	W22 Away
Visit	V3	V4	V5	V6	V7	-	-	-	V8	-	-	-
Arm												
Lebrikizumab Q2W/Q4W	500 mg (2 injections)	500 mg (2 injections)	250 mg	250 mg	250 mg	250 mg	250 mg	250 mg	250 mg	250 mg	250 mg	250 mg
Lebrikizumab Q2W/Q8W	500 mg (2 injections)	500 mg (2 injections)	250 mg	250 mg	250 mg	250 mg	250 mg	250 mg	250 mg	250 mg	250 mg	250 mg
PBO	2 PBO	2 PBO	1 PBO	1 PBO	1 PBO	1 PBO	1 PBO	1 PBO	1 PBO	1 PBO	1 PBO	1 PBO

Abbreviations: PBO = placebo; Q2W = every 2 weeks; Q4W = every 4 weeks; Q8W = every 8 weeks; W = week (as in W0; Week 0).

Note: Participants who are not comfortable self-administering IP away from the study site may come to the clinic for administration according to the “away” administration schedule. Enrollment of adolescents will be open-label, with all adolescents assigned to the lebrikizumab Q2W/Q4W treatment arm.

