**Table 6-3 Maintenance Period Dosing Schedule**

Week	W24 Clinic	W28 Away	W32 Away	W36 Away	W40 Clinic	W44 Away	W48 Away	W52 Away	W56 Clinic
Visit	V9	-	-	-	V10	-	-	-	V11
Arm									
Lebrikizumab Q2W/Q4W	250 mg	250 mg	250 mg	250 mg	250 mg	250 mg	250 mg	250 mg	No dose
Lebrikizumab Q2W/Q8W	250 mg	1 PBO	250 mg	1 PBO	250mg	1 PBO	250 mg	1 PBO	No dose
PBO	1 PBO	1 PBO	1 PBO	1 PBO	1 PBO	1 PBO	1 PBO	1 PBO	No dose

Abbreviations: PBO = placebo; Q2W = every 2 weeks; Q4W = every 4 weeks; Q8W = every 8 weeks; W = week (as in W0; Week 0).

Note: Participants who are not comfortable self-administering IP away from the study site may come to the clinic for administration according to the “away” administration schedule. Enrollment of adolescents will be open-label, with all adolescents assigned to the lebrikizumab Q2W/Q4W treatment arm.

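### Table 1-1 plans no pregnancy test before the in-clinic doses at Week 2 and Week 6, while every other scheduled dose has one

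*Protocol*

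**What the plan says.** Four parts of the protocol bear on this.

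- **Table 1-1, treatment rows.** The row "Dispense and administer IP at clinic" is marked at Visits 3 to 10, that is Weeks 0, 2, 4, 6, 8, 16, 24 and 40.
- **Table 1-1, laboratory rows.** The row "Pregnancy test (for WOCBP and all female adolescents") is marked at Visits 1, 3, 5, 7, 8, 9, 10, 11 and 801. It is blank at Visits 2, 4 and 6 and at unscheduled visits.
- **Footnote p.** It specifies "serum testing at screening and urine testing at subsequent visits prior to administering any IP". It then adds: "Additional pregnancy tests (beyond those required by the SoA) should be performed at any time during the study if a menstrual period is missed". Clinical suspicion and local or institutional rules are the other grounds for extra tests.
- **Section 8.4.** Site testing is referred back to the Schedule of Activities. Women of childbearing potential and all female adolescents are also told to do a urine test before taking IP away from the site.

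Table 6-2 ("Loading Dose and Induction Period Dosing Schedule") confirms that Weeks 2 and 6 are clinic doses. Week 2 is the second loading dose, given as two injections. Table 6-3 ("Maintenance Period Dosing Schedule") sets injections every 4 weeks from Week 24 to Week 52 in all arms, with placebo filling in for the Q8W arm.

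**The concern.** The protocol plans a urine test before each dose that a participant takes at home, yet none before two doses that staff give at the site early in treatment. No reason for the exception is stated.

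Pregnancy is an exclusion (Section 5.2, criterion 31). A participant known to be pregnant must be withdrawn (Section 7.2) and stops study treatment (Section 8.4). A pregnancy too early to detect at Visit 3 would meet its next marked test at Week 4, after the second loading dose. A test at Week 2 could prevent that dose and later ones, though it would not undo the Week 0 exposure. Section 4.3 describes the half-life of lebrikizumab as long, so a dose that could have been withheld is not cleared quickly.

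**Working it through.** There is no stated figure to reproduce. The check is a visit-by-visit comparison and a count of nominal intervals, ignoring visit windows.

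**Step 1. Clinic doses against marked tests (Table 1-1).** Both rows carry entries for all 13 visit columns, so the blanks are not lost cells.

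| Visit | Week | IP in clinic | Pregnancy test marked |
|---|---|---|---|
| 3 | 0 | yes | yes |
| 4 | 2 | yes | **no** |
| 5 | 4 | yes | yes |
| 6 | 6 | yes | **no** |
| 7 | 8 | yes | yes |
| 8 | 16 | yes | yes |
| 9 | 24 | yes | yes |
| 10 | 40 | yes | yes |

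Of 8 clinic doses, 6 have a marked test.

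**Step 2. All dosing days (Tables 6-2 and 6-3).**
- Weeks 0 to 22 every 2 weeks: 12 days.
- Weeks 24 to 52 every 4 weeks: 8 days.
- Total: 12 + 8 = 20.
- Away doses: Weeks 10, 12, 14, 18, 20, 22, 28, 32, 36, 44, 48 and 52, which is 12 days. If taken at home, each is preceded by the Section 8.4 urine test.
- Planned pre-dose coverage: 6 + 12 = 18 of 20. The remaining two are Weeks 2 and 6.

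**Step 3. Spacing of planned tests, Week 0 to Week 56.** The tests are the 18 above plus Week 56, so 19 tests and 18 intervals.
- Weeks 0, 4, 8: 2 intervals of 28 days.
- Weeks 8, 10, ..., 24: 8 intervals of 14 days.
- Weeks 24, 28, ..., 56: 8 intervals of 28 days.
- Maximum: 28 days. Time at 28-day spacing: 8 + 32 = 40 of 56 weeks. Time at 14-day spacing: 16 of 56 weeks.

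**Step 4. Which reading of footnote p fits.**
- The footnote speaks of tests beyond those the schedule requires, so it treats the marks as the required set.
- Visits 11 and 801 are marked although no IP is given there, so the marks do not follow dosing.
- Footnote s orders blood samples before dosing on a dosing day, yet the pharmacokinetic row is blank at dosing Visits 4, 6 and 7. That wording clearly sets order, not frequency, and footnote p is built the same way.
- From Visit 1 to Visit 11, the pregnancy-test row has the same marks as the row "Hematology/clinical chemistry laboratory", which suggests that the tests were placed at laboratory visits.

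So footnote p does not add tests at Visits 4 and 6.

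**Step 5. With a mark at Visits 4 and 6.** Coverage becomes 20 of 20 dosing days. There are 21 tests: Weeks 0 to 24 give 12 intervals of 14 days, matching the Q2W doses, and Weeks 24 to 56 keep 8 intervals of 28 days, matching the 4-weekly injections.

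**The case against.** The strongest reply is that the grid is deliberate. Marks at Weeks 0, 4 and 8 give 28-day testing, the same spacing that is accepted in Weeks 24 to 56, and nothing in the protocol says that site tests must match the dosing interval. Home doses need a test because no staff are present, whereas Visits 4 and 6 include review of adverse events and concomitant medication, and suspicion raised there triggers a test under footnote p. Contraception is mandatory (Section 5.1, criterion 8), with a serum test at screening and a urine test at Visit 3.

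Most of this stands, and it is why the risk is low. It does not explain the pattern. From Week 8 to Week 24, every two-weekly dose has a planned test, including the clinic doses at Weeks 8, 16 and 24, and in maintenance every injection has one. Only Weeks 2 and 6 fall outside, both early, and for-cause testing depends on someone noticing a reason. Table 15-1 lists the urine test as evaluated locally, so the absence of central laboratory sampling at these visits is no obstacle.

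Two stronger inferences should be resisted. A reader might take footnote p literally and conclude that it contradicts the grid; Step 4 of the working shows why that is the weaker reading. A reader might also infer that the test is lost when an away dose is given on site, since footnote h says: "Participants who are not comfortable self-administering IP away from the study site may come to the study site for administration". Section 8.4 words its test for dosing away from the site and Table 1-1 has no column for such doses, but nothing says that the test is dropped. No error is shown there.

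**Conclusion.** The point holds as a small gap against the protocol's own pattern of testing before each dose. Two of 20 scheduled dosing days, Weeks 2 and 6, have no planned pregnancy test beforehand. This rests on reading footnote p as governing marked visits only and on away doses being taken at home with the Section 8.4 test; the share given on site instead is not stated. The possible gain is detection up to 14 days earlier in each of two 28-day windows. The figures count planned tests and doses, not expected pregnancies. The documents do not support calling this a contradiction or a serious safety failing. It is a cheap improvement at the lowest level of importance, with no bearing on any endpoint, power or alpha.

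**What to change.** Add a mark at Visits 4 and 6 in the pregnancy-test row of Table 1-1, so that a local urine test precedes those doses. Reword footnote p to say: *urine testing at the marked visits, before any IP given at that visit*. Optionally, add that away doses given at the site are also preceded by a urine test.

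The cost is two extra local urine tests per woman of childbearing potential or female adolescent, at visits that already take place, plus one table and footnote edit. Under the optional sentence, a site test simply replaces the home test.

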## **2 Introduction**

### **2.1 Study Rationale**

To date, systemic corticosteroids (SCS) and surgery have been used to treat chronic rhinosinusitis (CRS) with nasal polyps (CRSwNP), which provide short-term relief and/or result in disease recurrence. Lebrikizumab is a monoclonal antibody that selectively inhibits interleukin (IL)-13 signaling. Blocking IL-13 signaling is expected to be beneficial for treating CRSwNP where IL-13 is a central cytokine involved in disease pathogenesis. Currently, dupilumab, omalizumab, and mepolizumab have been approved for the treatment of CRSwNP in adults, and despite these treatments, a proportion of patients still require rescue with SCS or surgery. There are currently no biologic treatments approved for CRSwNP in adolescents.

Lebrikizumab is being evaluated in this study (J2T-MC-KGBU), a pivotal Phase 3, multinational, multicenter, randomized, double-blind, placebo (PBO)-controlled, parallel group study to evaluate the efficacy and safety of lebrikizumab compared to PBO in participants with CRS with bilateral nasal polyps (NP) who receive background therapy with intranasal corticosteroids (INCS). This 72-week study will evaluate the efficacy of lebrikizumab in reducing the signs and symptoms of CRS with bilateral NP.

### **2.2 Background Information**

#### **2.2.1 Pathobiology and Clinical Manifestations of CRSwNP**

CRSwNP is a chronic inflammatory condition associated with significant morbidity and is estimated to affect 1% to 4% of the general population and 25% to 30% of patients with CRS (Stevens et al 2016; Fokkens et al 2020). CRSwNP is much less common in the pediatric population (Fokkens et al 2020; Tan et al.2013). CRSwNP is characterized by the loss of the immune barrier and increased or chronic inflammation in nasal passages. These conditions create increased nasal congestion and polyp formation. IL-4 and IL-13 induce activation of M2-type macrophages, which contribute to the pathogenesis of CRSwNP by inducing fibrin deposition, edematous remodeling, and polyp formation (Maspero et al 2022). The exact cause of NP is unknown, but allergy, asthma, infection, and aspirin sensitivity have been associated with this complex refractory disease in adults (Stevens et al 2016).

Nasal congestion is a major symptom in CRSwNP caused directly by physical obstruction from NP but can also be caused by mucosal inflammation either by irritants (eg, smoke, exhaust, or perfume) or allergens. IL-13-triggered inflammation causes venous engorgement, increased nasal secretions, and tissue swelling, further leading to airflow impairment and nasal congestion ([Naclerio et al 2010](#)).

### **2.2.2 Treatment of CRSwNP**

CRSwNP can lead to recurrent secondary bacterial infections needing multiple courses of systemic antibiotics, and resulting antibiotic resistance is not uncommon in this population ([Rosenfeld et al 2015](#)). The treatments of CRSwNP are predominantly SCS, INCS, and/or surgery. While these treatments do provide short-term relief, a recent meta-analysis reported that 18.6% of patients have more than 1 polyp removal surgery ([Loftus et al 2020](#)), and 35% of patients who underwent surgery for polyp removal had recurrence of NP at 6 months ([DeConde et al 2017](#)).

Currently, dupilumab, omalizumab, and mepolizumab have been approved for the treatment of CRSwNP in adults and despite these treatments a proportion of patients still require rescue with SCS or surgery. There are currently no biologics approved for the treatment of CRSwNP in adolescents.

